14.1. Source Data

Source documents and source data are considered to be the original documentation where subject information, visits consultations, examinations and other information are recorded. Documentation of source data is necessary for the reconstruction, evaluation and validation of clinical findings, observations and other activities during a clinical trial.

14.2. Access to Source Data

The site investigators and site staff will make all source data available to the DAIT/NIAID as well as to relevant health authorities. Authorized representatives as noted above are bound to maintain the strict confidentiality of medical and research information that may be linked to identified individuals.

15. Protocol Deviations

15.1. Protocol Deviation Definitions

Protocol Deviation – The investigators and site staff will conduct the study in accordance to the protocol; no deviations from the protocol are permitted. Any change, divergence, or departure from the study design or procedures constitutes a protocol deviation. As a result of any deviation, corrective actions will be developed by the site and implemented promptly.

Major Protocol Deviation (Protocol Violation) - A Protocol Violation is a deviation from the IRB approved protocol that may affect the subject's rights, safety, or well-being and/or the completeness, accuracy and reliability of the study data. In addition, protocol violations include willful or knowing breaches of human subject protection regulations, or policies, any action that is inconsistent with the NIH Human Research Protection Program's research, medical, and ethical principles, and a serious or continuing noncompliance with federal, state, local or institutional human subject protection regulations, policies, or procedures.

Non-Major Protocol Deviation - A non-major protocol deviation is any change, divergence, or departure from the study design or procedures of a research protocol that does not have a major impact on the subject's rights, safety or well-being, or the completeness, accuracy and reliability of the study data.

15.2. Reporting and Managing Protocol Deviations

The study site principal investigator has the responsibility to identify, document and report protocol deviations as directed by the study Sponsor. However, protocol deviations may also be identified during Quality Assurance review or during other forms of study conduct review.

A protocol deviation is any noncompliance with the clinical trial protocol, GCP, or protocol specific MOP requirements. The noncompliance may be either on the part of the subject, the site principal investigator, or other study personnel. Upon determination that a major protocol deviation has occurred, the study staff will a) notify the site Principal Investigator, b) notify the NIAID/DAIT Project Manager and c) will complete a Protocol Deviation form. Major protocol deviations will be determined in conjunction with the NIAID/DAIT Medical Monitor. It is the responsibility of the Protocol Chair and other study personnel to use continuous vigilance to identify and report major deviations within 5 working days of identification of Major Protocol Deviation, or within 5 working days of the scheduled protocol-required activity. Non-Major Protocol Deviations will be summarized and reported to DAIT every 3 months.

As a result of deviations, corrective actions are to be developed by the site and implemented promptly.

These practices are consistent with ICH E6:

4.5 Compliance with Protocol, Sections 4.5.1, 4.5.2, and 4.5.3

5.1 Quality Assurance and Quality Control, Section 5.1.1

5.20 Noncompliance, Sections 5.20.1, and 5.20.2.

All protocol deviations, as defined above, must be addressed in study subject data collection forms. A completed copy of the Protocol Deviation Form must be maintained in the Study File, as well as in the subject's chart.

Protocol deviations must be sent to the local IRB/IEC per their guidelines. The site principal investigator and other study personnel are responsible for knowing and adhering to their IRB requirements.

16. Ethical Considerations and Compliance with Good Clinical Practice

16.1. Statement of Compliance

This clinical study will be conducted using good clinical practice (GCP), as delineated in *Guidance for Industry: E6 Good Clinical Practice Consolidated Guidance*, and according to the criteria specified in this study protocol. Before study initiation, the protocol and the informed consent documents will be reviewed and approved by the IRB. Any amendments to the protocol or to the consent materials will also be approved by the IRB before they are implemented.

16.2. Informed Consent Process

The consent process will provide information about the study to a prospective participant and will allow adequate time for review and discussion prior to his/her decision. The principal investigator or designee listed on the Investigator of Record form will review the consent and answer questions. The prospective participant will be told that being in the trial is voluntary and that he or she may withdraw from the study at any time, for any reason. All participants will read, sign, and date a consent form before undergoing any study procedures. Consent materials will be presented in participants' primary language. A copy of the signed consent form will be given to the participant.

The consent form will be revised when important new safety information is available, the protocol is amended, and/or new information becomes available that may affect participation in the study.

Appendix A. Severity Scale for Local Vaccine Reactions (local reactogenicity events)

INJECTION SITE REACTIONS			
Grade			
	1	2	3
Swelling/ Induration/	Mild induration, able to move skin parallel to plane (sliding) and perpendicular to skin (pinching up)	Moderate induration, able to slide skin, unable to pinch skin; limiting instrumental activities of daily living	Severe induration, unable to slide or pinch skin; limiting arm movement limiting self-care activities of daily living
Redness/ erythema	Asymptomatic or mild symptoms; intervention not indicated	Moderate; minimal, local; limiting age-appropriate instrumental activities of daily living	Severe but not immediately life-threatening; hospitalization or prolongation of existing hospitalization indicated; disabling; limiting self-care activities of daily living
Pain/tenderness	Mild	Moderate pain; limiting instrumental activities of daily living	Severe pain; limiting self-care activities of daily living

Note:

Instrumental Activities of Daily Living refer to preparing meals, shopping for groceries or clothes,

using the telephone, managing money, etc.

Self-care Activities of Daily Living refer to bathing, dressing and undressing, feeding self, using the

toilet, taking medications, and not bedridden

Appendix B. Adverse Events Grading

Vital Signs	Mild (Grade 1)	Moderate (Grade 2)	Severe (Grade 3)	Potentially Life Threatening (Grade 4)
Fever* (°C) (°F)	38.0- 38.4 100.4- 101.1	38.5- 38.9 101.2- 102.0	39.0- 40.0 102.1- 104.0	>40.0 >104.0

*Oral temperature; no recent hot or cold beverages or smoking

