3.1. Description of Study Design

This is a single center, open label mechanistic study in which older adult subjects will receive Zoster vaccine recombinant, adjuvanted (Shingrix®). The study cohort will consist of 60, generally healthy older adults who will receive two doses of Shingrix®: 30 subjects between the ages of 50 to 60 years, and 30 subjects who are 70 years of age or above (shown below).

Enrollment:

N=60	50-60 year olds	N= 30	Shingrix®
	≥ 70 year olds	N= 30	Shingrix®

Once enrolled, subjects can withdraw from the study anytime. Subjects will be screened for health status by history and a targeted physical examination on the day of potential enrollment. Collected data will include demographic information, medical history, list of current medications and vaccination history. Subject will also receive a Shingrix® Vaccination Information Sheet.

Vaccination will occur on D0 after eligibility criteria have been confirmed and baseline blood has been obtained. Following administration of Shingrix®, symptoms and signs will be assessed in the clinic for at least 15 minutes after inoculation. Subjects will be followed for safety and immune responses after vaccination. Even though herpes zoster vaccine is administered as standard of care and is considered safe in subjects above 50 years of age, subjects will be asked to maintain a memory aid to record temperature and solicited systemic and local adverse events (AEs) for 7 days post each vaccination. The subject will record oral temperature around the same time each day with a thermometer provided by the clinic. The subject will use a ruler to measure the size of any localized reactions that may occur. The memory aid will be reviewed when the subject will return to the clinic within the first week after vaccination and examination of the injection site will be performed during these visits.

Additionally, unsolicited AEs will be reported for 30 days post each vaccination and SAEs for the duration of the study. During all visits, assessment of concomitant medications will be obtained and a targeted physical examination will be performed only if indicated, based on review of health status.

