7.4. Rescue Medications

Should an anaphylactic or hypersensitivity reaction occur, epinephrine (1:1000) and diphenhydramine intramuscular injections are readily available at clinic sites. If needed, the site will initiate emergency procedures as per their institution policy. If needed, participant will be transferred to the Emory University Hospital Emergency Department.

8. Study Procedures

Shingrix® vaccine will be administered in two doses (0.5 mL each, at D0 and D60) intramuscularly in the deltoid region of the arm. Aseptic technique will be used.

Blood will be drawn at D0 (pre-vaccination), and at D1, D3, D7, D14, D30, D60, D61, D63, D67, D74, D90 D180 and optional D270+ post vaccination. Stool will be collected at baseline D0 (pre-vaccination).

A targeted physical examination will be performed when deemed necessary.

A memory aid will be completed for symptom assessment (local and systemic) from Day 0 to Day 7 and from D60 to D67.

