8.3. Vaccination Visit (D0 - first dose of vaccination)

The purpose of the screening period is to confirm eligibility to continue in the study.

The following procedures and assessments will be conducted to determine participant eligibility:

1. Review inclusion/exclusion criteria
2. Review medical history, current medications and vaccination history
3. Record vital signs
4. Targeted physical examination if needed based on symptomatology and medical history
5. Draw blood tubes for analysis (pre-vaccination) and collect stool.
6. Administer first dose of Shingrix vaccine (0.5 mL) intramuscularly in the deltoid region of the preferred arm. Aseptic technique will be used.
7. Observe subjects for at least 15 minutes for any immediate hypersensitivity reactions.
8. Record vaccination in the Georgia Registry of Immunization Transactions and Services (GRITS).
9. Provide subjects with memory aid and other study related materials (thermometer and ruler to measure the size of any localized reactions that may occur) to record daily temperature and potential systemic and local side effects.

The visit will last around 1 ½ to 2 hours. No randomization is performed since all subjects, if eligible and wish to proceed with the study, will receive the first dose of the Shingrix® vaccine.

The Screening and Vaccination Visits may be combined into one visit if all activities can be completed in one visit. The combined screening/baseline visit will last around 2 – 2 ½ hours.

Subjects will be encouraged to take their oral temperature around the same time each day. Subjects will be instructed on how to use the memory aid and how to measure and record reactogenicity prior to leaving the clinic. Subjects will be instructed to notify the study center by telephone if they develop any severe reactions following vaccination. If the investigator deems the reaction severe enough, she/he will give further instructions on the proper course of action, including a return to the clinic for immediate evaluation if appropriate.

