8.4. Study Visits or Study Assessments

8.4.1. Scheduled Study Follow-up Visits

All subjects will return for follow-up visits on D1, D3, D7 (+/-1), D14 (+/-2), D30 (+/-7), D60 (second dose of vaccine), D61, D63, D67 (+/-1 from second vaccination), D74 (+/-2 from second vaccination), D90 (+/-7 from second vaccination), D180 (+/-14 from first vaccination), and an optional visit past 9 months (D270 +) from first vaccination. These visits will last 30 minutes.

At these visits, study personnel will:

1. Review current health status
2. Record change in medications or receipt of other vaccination (on optional later visit).
3. Note any health changes since last visit
4. Perform a physical examination and vital signs (only if indicated, based on review of health status).
5. Draw blood tubes for analysis
6. Ask subjects to report local and systemic AEs developing the day of any blood draw.
7. Inquire about SAEs.
8. Review memory aid information with subject and examine the vaccine site (on Days 1, 3, 7, and Days 61, 63, 67).

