8.4.2 Second Vaccination Visit (Day 60)

This visit will take approximately 2 hours. At this visit, study personnel will:

1. Review current health status.
2. Record change in medications.
3. Review eligibility criteria
4. Note any health changes since last visit.
5. Record vital signs
6. Perform a physical examination (only if indicated, based on review of health status).

7. Draw blood tubes for analysis.
8. Ask subjects to report local and systemic AEs developing the day of any blood draw.
9. Inquire about SAEs.
10. Administer second dose of Shingrix® vaccine.
11. Observe subject for at least 15 minutes for any immediate hypersensitivity reactions.
12. Record vaccination in the Georgia Registry of Immunization Transactions and Services (GRITS).
13. Provide subjects with memory aid and other study related materials (thermometer and ruler) to record daily temperature and potential systemic and local side effects.

Subjects will be encouraged to take their temperature around the same time each day. Subjects will be instructed on how to use the memory aid and how to measure and record reactogenicity prior to leaving the clinic. Subjects will be instructed to notify the study center by telephone if they develop any severe reactions following vaccination. If the investigator deems the reaction severe enough, she/he will give further instructions on the proper course of action, including a return to the clinic for immediate evaluation if appropriate.

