12.4.2 Collecting Adverse Events

Adverse events (including SAEs) may be discovered through any of these methods:

- Observing the subject.
- Interviewing the subject and using the memory aid.
- Receiving an unsolicited complaint from the subject.

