APPENDIX D. SCHEDULE OF EVENTS

Day	D -28 - D0	D0	D1	D3	D7 +/- 1	D14 +/- 2	D3 0 +/- 7	D60 + 7	D61	D63	D67 +/- 1*	D74 +/- 2*	D90 +/- 7*	D18 0+/- 14**	D27 0+** ***
Visit	Screen -ing	1	2	3	4	5	6	7	8	9	10	11	12	13	14
Informed Consent & HIPPA***	X														
Verify Eligibility Criteria	X	X						X							
PID assignment	X														
Demographic and Medical History (including medication and vaccine history).	X	X	X	X	X	X	X	X	X	X	X	X	X	X	X
Concomitant Medications	X%	X%	X	X	X	X	X	X	X	X	X	X	X	X	X
Vital signs (Oral Temperature, Pulse Rate, and BP)	X	X	(X)	(X)	(X)	(X)	(X)	X	(X)	(X)	(X)	(X)	(X)	(X)	(X)
Height and Weight	X														
Focused physical exam (only if indicated based on review of health status)	X	X	X	X	X	X	X	X	X	X	X	X	X	X	X
Vaccination		X						X							
Assessment of health status 15 minutes after administration of study vaccine		X						X							
Memory Aid Review			X	X	X				X	X	X				
Instruction given to study subjects on safety events and concomitant medications****		X	X	X	X	X	X	X	X	X	X	X	X	X	
Blood draw for Innate Assays and Adaptive Assays		X	X	X	X	X	X	X	X	X	X	X	X	X	X
Stool collection	X	X													
Adverse Events		X	X	X	X	X	X		X	X	X	X	X	X	
Serious Adverse Events		X	X	X	X	X	X	X	X	X	X	X	X	X	X

Footnotes:

%All current medications and medications taken within 30 days prior to day 0 of the study.

* Windows here are in relation to the second (D60) vaccination: D67 (+/-1 from second vaccination), D74 (+/-2 from second vaccination) and D90 (+/-7 from second vaccination).

** D180 +/- 14 days from first vaccination,

***Prior to study procedures

*****D270+, an optional visit at 9 months and beyond, after the first visit may occur.

Any Adverse Event (including – but not limited to- vaccine reactions and local or systemic reactogenicity events) of grade 2 or higher severity or serious adverse event (SAE) occurring after vaccination while the subject is still at the clinical site will be recorded and reported.

**** Instruction includes the following:

1. Subjects will be provided (on D0 and D60 only) with a written description of local and systemic vaccine reactions of mild, moderate and severe intensity and instructed to call the site to report reactogenicity events of grade 3 severity within 1 week following vaccination.

2. Subjects will also be instructed to promptly call the site if he/she develops any of the following:

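### Fever is graded only on measured oral temperature, but the plan asks for one reading a day at no set hour and does not say which reading is graded, so short fevers and peaks can be missed

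*Combined protocol and SAP*

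**What the plan says.** Appendix B defines four fever grades: 38.0 to 38.4 °C, 38.5 to 38.9 °C, 39.0 to 40.0 °C, and above 40.0 °C. Its footnote reads "Oral temperature; no recent hot or cold beverages or smoking". That note is sound in itself, but it does not say which of a participant's readings is graded.

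The reading schedule is set elsewhere:

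- Section 3.1: "The subject will record oral temperature around the same time each day with a thermometer provided by the clinic".
- Section 8.3, first dose: "Subjects will be encouraged to take their oral temperature around the same time each day".
- Section 8.4.2, second dose: "Subjects will be encouraged to take their temperature around the same time each day". The word oral is absent here.
- Section 8 (Study Procedures), window: "A memory aid will be completed for symptom assessment (local and systemic) from Day 0 to Day 7 and from D60 to D67".

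No section names a clock hour, asks for the day's maximum, or asks for a further reading when the participant feels feverish or shivers. Nothing forbids extra readings either, and the participant keeps the thermometer.

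Other routes to an adverse event exist. Section 8.4.1 has staff review the memory aid on D1, D3, D7, D61, D63 and D67, and has them "Ask subjects to report local and systemic AEs developing the day of any blood draw". Section 12.4.2 lists observation, unsolicited complaints and "Interviewing the subject and using the memory aid". Under Appendix D participants are "instructed to call the site to report reactogenicity events of grade 3 severity within 1 week following vaccination".

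The secondary endpoint (sections 3.3 and 13.2) contrasts related AEs and SAEs between doses in both cohorts. Section 13.4.4 analyses AE rates with frequency tables and Fisher's exact test. No endpoint is specific to fever.

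**The concern.** Fever differs from the other systemic reactions in this plan. Appendix C grades headache, fatigue, myalgia and shivering largely by interference with activity, which a participant can recall at the next visit. Appendix B grades fever on a number alone. If no reading was taken while the temperature was raised, a later interview cannot supply a grade, and the participant cannot know that the grade 3 cut-off for calling the site was reached.

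Any error from this source lowers the recorded rate or grade. If the same share of fevers goes unmeasured after each dose, the absolute difference between doses shrinks. If the share differs between doses, the difference can move either way. Two features of the plan leave room for that: the reading hour is the participant's choice and need not be the same after both doses, and sections 5.3 and 7.1.2 allow acetaminophen or NSAIDs for moderate to severe reactions without asking for a temperature first.

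**Working it through.** The plan states no rate, power or precision for fever, so there is no figure to reproduce. Two questions can be worked through: what a daily reading detects, and what that does to the comparison of doses.

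**1. Detection of one episode.** Input from the documents: one reading per day (sections 3.1, 8.3, 8.4.2). Assumptions: readings exactly 24 hours apart, one continuous fever of L hours inside the collection window, onset uniform over the 24 hours between readings, and no other reading taken. The episode then contains a reading with probability min(1, L/24).

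| L (hours, assumed) | Capture |
|---|---|
| 6 | 6/24 = 25% |
| 12 | 12/24 = 50% |
| 18 | 18/24 = 75% |
| 24 or more | 100% |

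The loss thus runs from none to large, depending on a duration that the documents do not give for fever. Section 5.1 gives a median of 2 to 3 days for most solicited reactions. If fever followed that, a typical episode would be caught. But the figure pools fever with reactions such as pain and fatigue and is not a fever duration. Uniform onset is also only an assumption: if onset clusters at a certain interval after vaccination, capture of a short fever depends strongly on the hour the participant happens to choose.

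**2. Grade of a detected episode.** This does not need the fever to be short. Grade 1 ends at 38.4 °C and grade 3 begins at 39.0 °C, a gap of 39.0 − 38.4 = 0.6 °C. A fever that peaks at 39.0 °C but stands at 38.4 °C at the chosen hour is recorded two grades lower. The documents give nothing from which to say how often that happens.

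**3. Comparison of doses.** Let p1 and p2 be the true fever proportions after doses 1 and 2, and s1 and s2 the capture probabilities, with no false positives. The recorded difference is s2·p2 − s1·p1.

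- If s1 = s2 = s, it equals s·(p2 − p1), which is shrunk but not reversed.
- If p1 = p2 = p, it equals p·(s2 − s1), a difference created by measurement alone.

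The second case needs capture to differ by dose. The documents leave that open but do not show it.

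**4. Do the other routes close the gap?** Memory-aid review recovers only what was written down. At follow-up visits without vaccination, Appendix D marks vital signs as optional and section 8.4.1 takes them only if indicated. Interviews and unsolicited complaints can reveal that someone felt feverish, but not the temperature. The grade 3 call depends on having measured one. These routes reduce the loss where they prompt a reading; they do not replace a missing one.

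**The case against.** The strongest reply is that a possibility is not a demonstrated bias. The memory aid is not among the documents and may already ask for more than the protocol text does. Participants are taught to measure and record reactogenicity, extra readings are not barred, and there are six memory-aid reviews plus the telephone instructions. The same schedule applies after both doses and in both cohorts, so the main effect would be lower absolute sensitivity. The endpoint is related AEs, of which fever is one component, and shivering is graded separately, so a febrile reaction can still register. All of this stands, and it limits the point to what can happen.

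A second reply is that readings prompted by symptoms make measurement more intensive where symptoms are more common. Section 5.1 gives shivering as 13.8% after dose 1 and 21.4% after dose 2, with fewer general symptoms from age 70. In an open-label study this could widen the dose and age contrasts. The cost is real but manageable: an extra reading adds a fever only if it measures 38.0 °C or more, and a separately recorded set-hour value keeps a like-for-like comparison.

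A reader might go further and infer a deflated fever rate from the 20.5% in section 5.1. The documents do not support that. The 20.5% is itself a recorded rate, and how temperature was taken in those trials is not stated. It also appears to cover both doses together, since headache there is 37.7% overall against 24.4% and 28.2% by dose, so a single-episode capture formula does not apply to it. Nor can one say that this study's rate is not comparable with it: if those trials also took one reading a day, it would be.

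**Conclusion.** The point holds as a gap in data collection. The plan asks for a daily temperature at no set hour, asks for neither a symptom-prompted nor a maximum reading, and does not say which reading Appendix B grades. Short fevers and peaks between readings can be missed, and the fever rate and grade may be understated. The size is unknown: capture is L/24 below 24 hours and complete from 24 hours, under the assumptions above, and L is not given. Understated peaks are possible at any duration and cannot be sized.

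Two stronger conclusions should not be drawn. The first is that fevers are being missed and the recorded rate is too low; no duration or within-day pattern in the documents shows this. The second is that a Grade 4 temperature, and with it a study hold, would go unseen. That needs a temperature above 40.0 °C that prompts no reading, call or report at any contact. The hold rule in section 11.5, as worded, also requires the event to be vaccine-related and unexpected.

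This is a low-cost improvement to one component of the safety summary. It does not affect the primary immunological analysis.

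**What to change.** Check the memory aid first, since it may already cover part of this. Then, in sections 3.1, 8.3 and 8.4.2 and in the memory aid:

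- Ask for one oral reading each day at the same hour after both doses, and add the word oral to section 8.4.2.
- Ask for an additional reading whenever the participant feels feverish or shivers.
- Record two values per day in separate fields: the set-hour value and the day's highest.

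In Appendix B, state that fever is graded on the highest oral temperature of each day. When fever is tabulated by dose and age cohort, show the set-hour value alongside as a check on unequal measurement.

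The cost is memory-aid wording, short edits in three sections and one sentence in Appendix B. The thermometer is already supplied, and no visits or staff are added. The downsides are a small burden on participants, a slightly higher recorded fever rate, and more readings in participants with symptoms, which the set-hour field allows the comparisons to check.
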